Treatment duration is approximately 6 months in the on-demand arm and from approximately 7 (200 days plus screening period of 2-3 weeks) to approximately 19 months in the prophylaxis arm. The maximum treatment period *in the Main Phase of this trial* is ~~24~~ 27 months. In the prophylaxis arm, all patients will continue in the *Main Phase* ~~trial~~ until the last patient *initiated in the prophylaxis arm* has received at least 50 EDs of N8-GP, thus all patients in the prophylaxis arm will receive at least 50 EDs of N8-GP and the average exposure to N8-GP will be more than 1 year. Patients enrolled in pathfinder™ 2 with the intention of entering the pathfinder™ 3 for major surgery can be enrolled in pathfinder™2 after the end of normal recruitment period. For the purpose of defining LPLV, the definition of LPLV *in the Main Phase* excludes these patients and the opening of the Extension Phase will not await these patients to complete 50 EDs in the trial. When *the Main Phase* is completed, all patients will be offered to continue treatment in the Extension ~~trial~~ Phase, if approved by country. As all patients will complete the *Main Phase* at the same time (or within a short timeframe) the transition of patients from *the Main Phase to the Extension Phase*, will be gradual and within a window of approximately 2 months *following the patient's visit schedule*. When the Extension Phase has opened and has been approved in the country the patient must at the next visit end the *Main Phase (Visit 13)* and continue into the *Extension Phase (Visit 14)*.

The distribution of patients *in the Extension Phase of the trial* will be as follows:

The Extension Phase of the trial includes two parts: part 1 and part 2. In part 1, patients who were on prophylaxis treatment every 4 days dosing with N8-GP during the Main Phase of the trial and with a 0-2 bleeding episodes during the last 6 months (180 days) before entering the Extension Phase, will be offered to be randomised to every 7 days or every 4 days treatment (2:1 randomisation). Patients with 3 or more bleeding episodes within the last 6 months of the Main Phase before entering the Extension Phase as well as patients with low bleeding rates who are unwilling to be randomised will continue with the same treatment regimen as in the Main Phase of the trial. Recruitment into the randomisation sub-group in the Extension Phase part 1 will stop

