18.10 Analyses of Extension Phase Data

Data from part 1 of the Extension Phase

*The main objective of part 1 of the Extension Phase is to investigate the safety and efficacy of every 7 day dosing by evaluating ABR for this dosing regimen and comparing it to the same historical bleeding episode rates as used in the primary analysis for the co-primary efficacy endpoint in the Main Phase. Prophylactic effect of every 7 day dosing will be concluded if the bleeding rate is significantly below 50% of the historical on-demand bleeding rate (i.e. significantly lower than 12) as well as within 25% of the historical prophylaxis bleeding rates (i.e. significantly lower than $6.8 * 1.25 = 8.5$). Since both must be met in practice it must be shown that the bleeding rate is significantly lower than 8.5.*

An analysis similar to that for the co-primary endpoint in the Main Phase will be carried out for the bleeding episodes in the two randomised treatment regimens during the Extension Phase part 1, adding treatment regimen as a factor to the model. Subjects switching from the every 7 day dosing arm to the non-randomised every 4 day dosing arm will be handled as withdrawals in this analysis. The imputation for withdrawals will be similar to that for the Main Phase, except that planned maximum duration is now 6 months.

Estimates of the annualised bleeding rates for each randomised regimen will be provided with 95% confidence intervals. Prophylactic effect of every 7 day dosing will be concluded if the upper limit of the 95% CI is below 8.5. In addition, the two randomised treatment regimens will be compared by reporting the estimated ratio between the two randomised treatment regimens with corresponding 95% confidence interval.

As for the co-primary endpoint in the Main Phase, a sensitivity analysis will be carried out where bleeding episodes for withdrawals are not imputed.

ABR based on accumulated number of bleeding episodes (Main Phase + Extension Phase part 1) will be evaluated for the every 4 day dosing regimens combined, i.e., combining the randomised and non-randomised arm. The model used will be the same as for the primary analysis of the Main Phase data.

Only treatment requiring bleeding episodes will be considered in the above evaluations of ABR

Incidence rate of FVIII-inhibitor and haemostatic effect of N8-GP when used for treatment of bleeding episodes will be evaluated based on accumulated data (Main Phase + Extension Phase part 1).

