5.3.1 Prophylaxis

...

Other changes of the dose or dosing interval for prophylaxis are not allowed within *the main phase of the trial*. However, extra doses of N8-GP will be administered if a patient experiences a treatment requiring bleeding episode or in case of minor surgery.

Extension Phase part 1: The prophylaxis dose of N8-GP is administered in the non-randomised group every 4 days or in the randomised group every 4 day or every 7 day depending on which treatment arm the patient is allocated to. Based on the bleeding pattern, the Investigator may change the every 7 day prophylaxis treatment to an every 4 day treatment regimen (the non-randomised arm) *at any time*. ~~but~~ Changing vice versa is not permitted. *In addition the Investigator must monitor the patient on an on going basis and change patients from every 7 day prophylaxis treatment to an every 4 day treatment regimen in accordance with the following rule. A patient on every 7 day prophylaxis must be switched back to every 4 day prophylaxis if either of the following criteria are met over a 8 week period:*

- *Two or more spontaneous bleeding episodes*
- *One severe bleeding episode requiring hospitalisation.*

Novo Nordisk will monitor that patients are switched from the every 7 day prophylaxis treatment to an every 4 day treatment regimen adhering to the rule mentioned above. Novo Nordisk will furthermore monitor the number of patients switching from every 7 day to every 4 day treatment regimen and will terminate the 7 day treatment arm if the below rule is met:

- *If at least 15 out of 30 patients (or 50% of 30 or more) whom have been randomised to the every 7 day treatment arm are switched back to the every 4 day treatment arm, then the every 7 day treatment arm will be closed and all remaining patients will be switched to every 4 day treatment.*

...

Extension Phase part 2: During this period it is possible to ~~adjust~~*change* the prophylaxis treatment of patients to *every 4 day or 7 day treatment*~~an individualised regimen. Treatment regimens ranging from once weekly to every 4 day will be allowed: every 4 day, every 5 day, every 6 day or every 7 day.~~ For deciding to change a regimen it is strongly recommended to follow *the Investigator must monitor the patient on an on going basis and follow the below* ~~guidelines~~*rules for change of regimen:*

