1.1 Trial information

This phase 3 trial is a multi-centre, multi-national, open-label, non-randomised trial evaluating safety, pharmacokinetics and clinical efficacy of NNC 0129-0000-1003 (hereafter referred to as N8-GP) when used for treatment of bleeding episodes and for long-term prophylaxis. The trial consists of a Main Phase followed by an Extension Phase part 1 and part 2. In the main phase, patients in the prophylaxis arm were receiving one single bolus dose of 50 U/kg body weight (BW) of N8-GP every 4 days (96 hours interval).

In the extension part 1, patients with a low bleeding rate on every 4 day prophylaxis in the main phase have the possibility of being randomised to either 50 U/kg BW every 4th day or to 75 U/kg BW once weekly dosing. If the patient for the last 6 months (180 days) prior to Visit 13/14 only had 0 - 2 bleeding episodes, the patient was eligible for randomisation. Patients who were not eligible to be in the randomised arm or patients who are eligible but unwilling to be randomised can stay on the same regimen as in the Main phase.

In the extension phase part 2, patients with a low bleeding rate (0-2 bleeding episodes during the last 6 months) on every 4 day prophylaxis have the possibility of changing to 75 U/kg BW once weekly dosing regimen. Patients who has been on 75 U/kg BW once weekly dosing during extension phase part 1 can continue on this regimen arm or change back to either 50 U/kg BW every 4th day if the patients want to. Patients on once weekly dosing who have more than 2 spontaneous bleeds within a 8 week period or are hospitalised due to a bleed need to change back to every 4 days regimen according to the protocol.

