2.2 Statistical Methods

2.2.1 General Considerations

Novo Nordisk A/S will be responsible for the statistical analysis. All tests will be performed as 1-sided tests on 2.5% significance level. All bleeding endpoints will be evaluated based on bleeding episodes requiring treatment with N8-GP. Non-treatment requiring bleeding episodes that coincide with regular prophylaxis doses are not included in the analyses.

Multiple bleeding locations occurring from the same event (e.g. due to a bicycle accident) or at the same time point will be counted as one bleeding episode and only one haemostatic response will be considered for the bleeding episode. In case different responses were registered for different bleeding locations in such a bleeding episode, the worst response will be used in the analysis. As stated in the protocol, a re-bleed is defined as a worsening of symptoms in the same location after an initial period of improvement, either on treatment or within 72 hours after stopping treatment. If a bleed occurs in the same location later than 72 hours after stopping the treatment it is

considered a new bleed. Re-bleeds will only be considered for joint bleeds since the specific location for other bleeds e.g. in subcutaneous are not captured in the database.

In the sub analyses of annualised bleeding rate where there are less than 5 patients in a sub-group, model based estimation will not be done. If no bleedings occur in a sub-group, then the confidence interval will not be calculated.

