For patients who were withdrawn in the Pivotal part the planned exposure time will be until the end of the pivotal part as described above. For patients who were withdrawn in the main part after the pivotal part ended, the maximum expected exposure time will be used, i.e. 100 weeks as this is the maximum duration for main phase. For patients withdrawn during extension phase part 1, the planned exposure is 24 weeks (duration of extension phase part 1) added to the actual exposure in main

For calculations only including the randomised period, the planned exposure time will be the time from visit 14 to visit 17, i.e. 24 weeks. Patients that change from Q7D to non-randomised part of Q4D will have their bleeds imputed using a planned exposure time of 24 weeks using the same approach as in the pivotal part of the trial even though they are not withdrawn from the study. This is to avoid bias for randomized Q7D caused by patients withdrawing due to high bleeding rate.

Calculations of ABR for extension phase part 2:

For patients withdrawn prior to extension phase part 2, planned exposure is calculated as explained above. For patients withdrawing during extension phase part 2, planned exposure in extension phase part 2 will be calculated using the overall cut-date (15Aug2017) as planned end date. The actual exposure time in main and extension phase part 1 is added to the planned exposure time in extension phase part 2, to get the overall planned exposure time for a withdrawn patient.

Planned exposure time is only relevant for the treatment regimen the patient is on, when being withdrawn. Time on other regimens and time in surgery trial is subtracted when calculating planned exposure time.

For patients who withdrew within 1 month, imputation will be conducted by assuming an annualised bleeding rate of 24 (bleeds per year) for the missing period. This also applies to change from Q7D to Q4D in the randomised part of extension phase part 1.

Estimates of the annualised bleeding rates for each regimen will be provided together with the 95% confidence intervals as described in the protocol.

Sensitivity analyses:

Analysis applying a different model

A sensitivity analysis based on a negative binomial regression model with number of bleeding episodes requiring treatment as the outcome variable, and adjusting for exposure time will be performed.

Analysis without imputation to planned trial duration

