2.10 Analyses of Extension Phase Data

Data from part 1 of the Extension Phase

The main objective of part 1 of the Extension Phase is to investigate the safety and efficacy of every 7 day dosing by evaluating ABR for this dosing regimen and comparing it to the same historical bleeding episode rates as used in the primary analysis for the co-primary efficacy endpoint in the Main Phase. Prophylactic effect of every 7 day dosing will be concluded if the bleeding rate is significantly below 50% of the historical on-demand bleeding rate (i.e. significantly lower than 12) as well as within 25% of the historical prophylaxis bleeding rates (i.e. significantly lower than $6.8 \times 1.25 = 8.5$). Since both must be met in practice it must be shown that the bleeding rate is significantly lower than 8.5.

An analysis similar to that for the co-primary endpoint in the Main Phase will be carried out for the bleeding episodes in the two randomised treatment regimens during the Extension Phase part 1, adding treatment regimen as a factor to the model. Subjects switching from the every 7 day dosing arm to the non-randomised every 4 day dosing arm will be handled as withdrawals in this analysis.

The imputation for withdrawals will be similar to that for the Main Phase, except that planned maximum duration is now 6 months.

Estimates of the annualised bleeding rates for each randomised regimen will be provided with 95% confidence intervals. Prophylactic effect of every 7 day dosing will be concluded if the upper limit of the 95% confidence intervals (CI) is below 8.5. In addition, the two randomised treatment regimens will be compared by reporting the estimated ratio between the two randomised treatment regimens with corresponding 95% confidence interval.

As for the co-primary endpoint in the Main Phase, a sensitivity analysis will be carried out where bleeding episodes for withdrawals are not imputed.

ABR based on accumulated number of bleeding episodes (Main Phase + Extension Phase part 1) will be evaluated for the every 4 day dosing regimens combined, i.e., combining the randomised and non-randomised arm. The model used will be the same as for the primary analysis of the Main Phase data.

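### The planned Q7D:Q4D bleeding-rate ratio in extension part 1 is biased against Q7D, because only Q7D has bleed-triggered switches and the switchers' bleeds are extrapolated

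*SAP*

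**What the plan says.** **Who is randomised.** SAP 1.1 looks at the 180 days before Visit 13/14: if he "only had 0 - 2 bleeding episodes, the patient was eligible for randomisation". Protocol 5.1 (Amendment 13) sets the allocation at 2:1, Q7D to Q4D.

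**Who can switch.** Protocol 5.3.1 (Amendment 14) says: "A patient on every 7 day prophylaxis must be switched back to every 4 day prophylaxis if either of the following criteria are met" over an 8-week period. The criteria are two or more spontaneous bleeds, or one severe bleed that needs hospitalisation. The investigator may also move a Q7D patient to Q4D at any time on his bleeding pattern. The reverse move is barred. Twice-weekly dosing in the extension is open only to patients already on it in the Main Phase. Randomised Q4D patients therefore have no bleed-triggered change of regimen.

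**How switchers are analysed.** Protocol 18.10: "Subjects switching from the every 7 day dosing arm to the non-randomised every 4 day dosing arm will be handled as withdrawals in this analysis". SAP 2.2.2: "Patients that change from Q7D to non-randomised part of Q4D will have their bleeds imputed using a planned exposure time of 24 weeks". If the switch comes within 1 month, the missing period is filled at 24 bleeds per year. The stated aim is to avoid favouring Q7D when frequent bleeders leave it.

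**What is reported.** The decision rule in SAP 2.10 is that the upper 95% limit of the Q7D rate lies below 8.5. Beyond that, "the two randomised treatment regimens will be compared by reporting the estimated ratio between the two randomised treatment regimens", with a 95% confidence interval. The one sensitivity analysis that SAP 2.10 names for part 1 drops the imputation.

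**The concern.** A forced switch happens because bleeds have just occurred. The observed rate is then at a local high, and the rule carries it forward to 24 weeks. A Q4D patient with the same cluster stays in his arm and contributes the quiet weeks that follow. The rule works in one arm only, so its effect does not cancel in the ratio.

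The SAP guards against bias in favour of Q7D but does not consider bias the other way. At stake is the only randomised efficacy contrast in the trial: a reported ratio of 1.2 or 1.3 could be read as evidence that weekly dosing protects less well when the analysis rule alone would produce it.

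**Working it through.** **1. The plan's own figure.** The documents give no sample size, power or expected ratio for the part 1 comparison. The only design figure for the bleeding rate is the Main Phase power in Protocol 18.1 (Amendment 6): 79% for a true rate of 7.0/year, over-dispersion 5, 120 patients for about 1 year, limit 8.5. By the normal approximation, Φ((8.5 − 7.0)/√(7.0 × 5/120) − 1.96) = Φ(2.78 − 1.96) = 79.3%, which agrees. The other rows of that table also reproduce (89.1, 97.0, 87.4 and 71.8%, against 89, 97, 87 and 72%).

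**2. The mechanism by hand.**
- Q7D patient with spontaneous bleeds in weeks 5 and 8, switched at week 8: he is entered with 2 × 24/8 = 6 bleeds in 24 weeks.
- The same patient in Q4D is entered with 2 bleeds plus those seen in the other 16 weeks. At an illustrative 4/year that is 4 × 16 × 7/365.25 = 1.2 more, so 3.2 in all.
- Q7D patient with two bleeds by week 3: the 1-month rule adds 24 × 21 × 7/365.25 = 9.7, giving 11.7. Plain extrapolation would give 2 × 24/3 = 16. The 1-month rule softens the effect but does not remove it.

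**3. Size, by simulation with equal regimens.**

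From the documents: selection on 0–2 bleeds in 180 days, 24 weeks of follow-up, a switch for two spontaneous bleeds within 8 weeks in Q7D only, and the two imputation rules. Assumed: gamma-distributed patient rates before selection, either 6.8/year with over-dispersion 5 (shape k from 1 + 6.8/k = 5, so k = 1.7) or 4/year with shape 1, and the spontaneous share. Severe-bleed and discretionary switches are not modelled.

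| Analysis, true ratio 1.00 | 40% spontaneous | 60% | 80% |
|---|---|---|---|
| Planned ratio, immediate switch, 6.8/year | 1.14 | 1.26 | 1.36 |
| Planned ratio, immediate switch, 4/year | 1.12 | 1.23 | 1.34 |
| Planned ratio, switch at next scheduled visit, both populations | 1.09–1.10 | 1.17–1.21 | 1.23–1.28 |

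With immediate switching, 6–28% of Q7D patients switch; with switching at the next visit, 4–19%.

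A separate set of runs took spontaneous shares of 40, 67 and 100%, fixed rates of up to 6.8/year and gamma rates with means of 2–6.8/year. The planned ratio ranged from 1.04 to 1.53 and was above 1 in every scenario. With a fixed 2/year and all bleeds spontaneous, switchers whose true rate is 2.0/year are entered at 10.6/year.

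**4. The alternatives, true ratio 1.00.**
- No imputation: 1.00 if all patients share one rate, but 0.88–0.99 in the selected, heterogeneous populations of the separate runs (about 0.9–0.98 at 40–80% spontaneous). Frequent bleeders leave early and contribute less time, which lowers the pooled Q7D rate.
- All bleeds observed over 24 weeks by randomised arm: 0.99–1.01.

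**5. True ratio 1.30.** The planned ratio averages about 1.47–1.77. The all-observed ratio averages about 1.21–1.27, because time after a switch is spent on Q4D.

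**A discrepancy on the trigger.** The runs use the Protocol's two or more spontaneous bleeds. SAP 1.1, describing part 2, gives more than 2. The two passages must be reconciled; a rarer trigger would mean fewer switches and a smaller bias.

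**The case against.** Several points on the other side stand.

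- **Role of the ratio.** Protocol 5.2 gives control of season effects as the reason for the Q4D group. The decision rests on Q7D against 8.5; the ratio is an addition with no hypothesis, margin or power. For the 8.5 rule, over-counting Q7D bleeds is conservative. In the populations of the table the imputed Q7D rate was 2.6–5.0/year against a true 2.3–3.7, well under 8.5.
- **Timing.** A reader might infer that a patient must leave Q7D at the instant of his second bleed. The documents set a criterion over 8 weeks but no instant. Table 2-3 lets the change be made at any visit, scheduled at weeks 4, 8, 12, 16 and 24; unscheduled visits are possible, and milder bleeds may be treated at home without contacting the site. Immediate switching is therefore the upper case.
- **Estimand.** After a switch the patient is on Q4D, so his later bleeds say nothing about the Q7D rate. Erring against Q7D is defensible when the switch rule was added over a regulatory concern about break-through bleeding.
- **Precision.** With an assumed 40:20 patients, the interval lies wholly above 1 in 2–12% of equal-regimen trials, against about 2% without switching. The harm is mainly a displaced estimate.

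One point stands only in part. SAP 2.2.2 adds a negative binomial model. Fitted to unimputed bleeds and on-regimen time, such a model gave 0.99–1.02 in all 12 equal-regimen runs. But the SAP does not say that it uses unimputed counts or that it covers the part 1 ratio.

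**Conclusion.** The Q7D:Q4D ratio planned for part 1 is biased upward, against Q7D. The asymmetry comes from the documents. The size depends on inputs they do not give: with equal regimens, the assumed rates and 40–80% spontaneous bleeds, the ratio averages about 1.1–1.4 with immediate switching and about 1.1–1.3 with switching at the next scheduled visit. The direction did not change in any scenario run. The no-imputation check leans the other way, at about 0.9–0.98, so the two part 1 analyses in SAP 2.10 fall on either side of the truth and neither is centred on it.

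Two stronger readings are tempting and not supported. One is that the weekly regimen's efficacy conclusion is unsafe: it is not, because a pass against 8.5 is reached despite the over-counting. The other is that the randomised comparison cannot be interpreted and the imputed analysis must go: the bias has a known direction, the data to examine it exist, and which estimand should lead is open to debate.

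**What to change.** In SAP 2.10 and Protocol 18.10:

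1. Keep the imputed analysis for the Q7D rate against 8.5.
2. Beside the imputed ratio, add a Q7D:Q4D ratio with 95% confidence interval from all treated bleeds observed between Visit 14 and Visit 17, by randomised regimen. Include bleeds and time after a switch, with log observed time as offset.
3. Label it *start Q7D with switch-back allowed*. SAP section 2 says part 1 has already been analysed and reported, so label it supplementary as well.
4. State that the imputed ratio is biased upward, and that the added ratio mildly attenuates a true difference (1.30 reads about 1.21–1.27).

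The cost is one labelled model and a few lines of text. SAP 2.2.2 itself notes that switchers have not left the study, and Protocol 8.2.1 has treated bleeds entered in the eDiary throughout the trial, so no new data are needed. The switch rule is not touched.
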